7.9.2 Pharmacodynamic Analysis

CCI

7.10 Other Outcomes

CCI

CCI

7.11 Safety Analysis

7.11.1 Adverse Events

Adverse events will be coded using the Medical Dictionary for Regulatory Activities (MedDRA) Version 20.0 or later (based on version at time of database lock). Treatment-emergent AEs are defined as: AEs that occur after the first dose of MLN0128 and within 30 days after the last dose of MLN0128.

Treatment-emergent AEs will be tabulated by MedDRA system organ class and preferred term and will include the following categories

- Treatment-emergent adverse events.
- Drug-related TEAEs.
- Grade 3 or higher TEAEs.
- Grade 3 or higher drug-related TEAEs.
- Most commonly reported TEAEs (at least 10% in any arm, sorted by preferred term).
- Serious TEAEs.
- Serious drug-related TEAEs.
- The most commonly reported treatment-emergent AEs by preferred term (at least 10% of patients).
- Most frequent non-serious TEAEs (>5% of patients in both cohorts sorted by preferred term).

Patients reporting the same event more than once will have that event counted only once within each system organ class, and once within each preferred term.

Adverse events of interest will be tabulated for the following:

Adverse event of interest	MedDRA Preferred Term	
Asthenic Conditions	Asthenia, Decreased activity, Fatigue, Malaise, Sluggishness (modified HLT)	
Mucosal Inflammation	Enanthema	Allergic stomatitis
	Mucosa vesicle	Aphthous ulcer
	Mucosal atrophy	Lip erosion
	Mucosal discolouration	Lip ulceration
	Mucosal dryness	Mouth ulceration
	Mucosal erosion	Oral mucosa erosion
	Mucosal exfoliation	Palatal ulcer
	Mucosal haemorrhage	Stomatitis
	Mucosal hyperaemia	Stomatitis haemorrhagic
	Mucosal hypertrophy	Stomatitis necrotising
	Mucosal induration	Mucosal pigmentation
	Mucosal inflammation	Mucosal roughness
	Mucosal membrane hyperplasia	Mucosal toxicity
	Mucosal necrosis	Mucosal ulceration
	Mucosal pain	Mucous membrane disorder
	Oedema mucosal	Leukoplakia
	Mucosal infection	Drug eruption
	Mucosal excoriation	Fixed eruption
	Erythroplasia	Mucocutaneous haemorrhage
	Burning sensation mucosal	
Paraesthesia mucosal		
Rash	Mucocutaneous rash	Rash papular
	Nodular rash	Rash rubelliform
	Rash	Rash scarlatiniform
	Rash erythematous	Rash vesicular
	Rash generalised	Rash maculovesicular
	Rash macular	Rash morbilliform
	Rash maculo-papular	

For the phase 1 portion a by-subject listing of DLTs in Cycle 1 will be generated.

The number and percentage of subjects experiencing treatment emergent AEs resulting in discontinuation of study drug (action on study drug=DISCONTINUED FROM STUDY) will be summarized by MedDRA system organ class, and preferred term.

A by-subject listing of treatment-emergent AEs resulting in discontinuation of study drug and treatment-emergent AEs resulting in dose modifications (held or reduced) will be generated.

A by-subject listing of the deaths will be presented. An on-study death is defined as a death that occurs between the first dose of study drug and within 30 days of the last dose of study drug.

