MLN0128 + Exemestane (Any Country)/Fulvestrant (US Only) Safety Cohort 2: Six patients will receive MLN0128 capsule formulation based on milled API, either 4 or 2 mg QD based on the safety observed in Cohort 1, in combination with either exemestane or fulvestrant. Serial PK samples will be collected as outlined for Cohort 1. After the last patient completes Cycle 1, a safety and tolerability assessment will be performed.

4.4.2 Phase 2

In the phase 2 portion of the study, the safety and efficacy of MLN0128 in combination with either exemestane (any country) or fulvestrant (US only) will be evaluated. Patients will be administered MLN0128 at either 4, 3, or 2 mg QD in combination with either exemestane (any country) or fulvestrant (US only), depending on the outcome of the safety and tolerability analysis performed in the phase 1b portion of the study.

Another safety and tolerability assessment will be performed during the phase 2 portion of the study where the first 6 patients treated with MLN0128 (either 4 mg, 3 mg, or 2 mg QD) in combination with exemestane or fulvestrant who have completed 2 cycles of treatment with MLN0128 will be evaluated for TEAEs. Enrollment of patients into the study will continue during this safety and tolerability assessment.

Patients will be enrolled into one of 2 parallel cohorts, depending on the quality and/or duration of their prior response to everolimus in combination with either exemestane (any country) or fulvestrant (US only) as follows:

Everolimus-Resistant Cohort: This is a cohort of 56 response-evaluable patients who have progressed on treatment with everolimus in combination with either exemestane (any country) or fulvestrant (US only) without achieving an objective response (CR or partial response) or after achieving SD for <6 months as their best response. Patients will receive MLN0128 in combination with the same dose of the previously administered treatment (exemestane [any country] or fulvestrant [US only]).

Everolimus-Sensitive Cohort: This is a cohort of 48 response-evaluable patients who have progressed on treatment after achieving a CR or partial response of any duration, or SD \geq 6 months with prior everolimus treatment in combination with either exemestane (any country) or fulvestrant (US only). Patients will receive MLN0128 in combination with the same dose of the previously administered treatment (exemestane [any country] or fulvestrant [US only]).

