6.0 DETERMINATION OF SAMPLE SIZE

Phase 1b

The safety and tolerability of MLN0128 in combination with either exemestane or fulvestrant will be evaluated. Patients will be enrolled as follows:

- In Part 1 of the phase 1b portion of the study, up to 6 patients will be enrolled into the MLN0128 + Exemestane Safety Cohort and up to 6 patients will be enrolled into the MLN0128 + Fulvestrant Safety Cohort. The number of patients is based on clinical considerations.
- In Part 2 of the phase 1b portion of the study, 6 patients will be enrolled into MLN0128 + Exemestane/Fulvestrant Safety Cohort 1, and 6 patients will be enrolled into MLN0128 + Exemestane/Fulvestrant Safety Cohort 2. The number of patients is based on clinical considerations.

Phase 2

The sample size for each cohort in the phase 2 portion of the study is based on a standard Simon two-stage design. A Bayesian predictive probability design was used to allow multiple interim analyses to stop early for futility [1]. See Section 6.0 for sample size assumptions. Up to 56 response-evaluable patients will be enrolled in the Everolimus-Resistant Cohort. In the Everolimus-Sensitive Cohort, up to 48 response-evaluable patients will be enrolled.

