7.2 Analysis Sets

7.2.1 Safety Population

Safety population: patients who receive at least 1 dose of study drug. All safety analyses will be performed using the safety population.

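### The SAP's frequent non-serious TEAE table requires more than 5% in both cohorts, so it omits terms that are frequent in only one

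*SAP*

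**What the plan says.** SAP 7.11.1 opens its list of adverse-event tables with "Treatment-emergent AEs will be tabulated by MedDRA system organ class and preferred term and will include the following categories". Most entries (all TEAEs, drug-related, Grade 3 or higher, serious, and their drug-related subsets) have no frequency cut-off. Three entries do:

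- "Most commonly reported TEAEs (at least 10% in any arm, sorted by preferred term", an any-arm rule;
- "The most commonly reported treatment-emergent AEs by preferred term (at least 10% of patients", an overall rule with no arm or cohort condition;
- "Most frequent non-serious TEAEs (>5% of patients in both cohorts sorted by preferred term", the rule at issue.

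The two cohorts are those of phase 2. SAP 4.4.2 says: "Patients will be enrolled into one of 2 parallel cohorts, depending on the quality and/or duration of their prior response to everolimus". Their planned sizes are in SAP 6.0: "Up to 56 response-evaluable patients will be enrolled in the Everolimus-Resistant Cohort" and "In the Everolimus-Sensitive Cohort, up to 48 response-evaluable patients will be enrolled". SAP 7.2.1 adds "All safety analyses will be performed using the safety population", so the table's denominators are all treated patients, not the response-evaluable ones. Protocol 8.1.8 lists the adverse-event summaries but has no non-serious table and no 5% threshold. The table is an SAP addition, and only the SAP defines it.

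**The concern.** A table of the most frequent events should show events that are frequent. A both-cohorts condition works differently: the cohort with the lower count decides whether a term is shown, and the rate in the other cohort does not matter. The same list already contains wording for an any-arm cut and for an overall cut, and this entry uses neither.

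The cohorts are defined by prior response to everolimus, not by study dose, and SAP 7.1.1 shows both at the same MLN0128 dose. There is no evident safety reason to require a term to pass the line in each. This is also the only listed table that separates non-serious from serious events. A term it omits has no separate non-serious count in any other planned table.

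**Working it through.** The SAP states no figure to reproduce here. The check is what the rule does to the list of terms.

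**Inputs.** Threshold above 5% in both cohorts (SAP 7.11.1). Cohort sizes 56 and 48 (SAP 6.0), used as an assumption for the safety-population sizes, which the documents do not give. The true event rates below are also assumptions, chosen to show a range.

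**Smallest count that passes.**
- Resistant, n = 56: 2/56 = 3.6% fails and 3/56 = 5.4% passes.
- Sensitive, n = 48: 2/48 = 4.2% fails and 3/48 = 6.25% passes.
- Pooled, n = 104: 5/104 = 4.8% fails and 6/104 = 5.8% passes.

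**Example counts under three readings.**

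| Resistant | Sensitive | Pooled | Both | Either | Pooled >5% |
|---|---|---|---|---|---|
| 11/56 (19.6%) | 2/48 (4.2%) | 13/104 (12.5%) | omitted | listed | listed |
| 2/56 (3.6%) | 12/48 (25.0%) | 14/104 (13.5%) | omitted | listed | listed |
| 5/56 (8.9%) | 0/48 | 5/104 (4.8%) | omitted | listed | omitted |
| 3/56 (5.4%) | 3/48 (6.25%) | 6/104 (5.8%) | listed | listed | listed |

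**Listing probabilities.** Treat the cohorts as independent. Let A = P(X ≥ 3) for X ~ Binomial(56, p_R) and B = P(Y ≥ 3) for Y ~ Binomial(48, p_S). Then P(both) = A × B, P(either) = 1 − (1 − A)(1 − B), and P(pooled) = P(X + Y ≥ 6).

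For a true rate of 8% in each cohort:
- A = 1 − (0.0094 + 0.0457 + 0.1092) = 0.836
- B = 1 − (0.0183 + 0.0763 + 0.1559) = 0.750
- P(both) = 0.836 × 0.750 = 0.63
- P(either) = 1 − 0.164 × 0.250 = 0.96

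The other rows follow in the same way:

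| True rates (Resistant, Sensitive) | A | B | Both | Either | Pooled |
|---|---|---|---|---|---|
| 8%, 8% | 0.836 | 0.750 | 63% | 96% | 85% |
| 10%, 10% | 0.928 | 0.871 | 81% | 99% | 95% |
| 15%, 15% | 0.993 | 0.982 | 97.5% | about 100% | 99.9% |
| 10%, 4% | 0.928 | 0.301 | 28% | 95% | 77% |
| 15%, 3% | 0.993 | 0.174 | 17% | 99% | 94% |

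The first three rows show loss by chance alone. In the last two, most of the loss comes from the assumed difference between cohorts.

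**Sensitivity to the denominator.** The cut stays at 3 patients up to n = 59 (3/59 = 5.1%) and becomes 4 at n = 60 (3/60 is exactly 5% and fails). A somewhat larger safety population moves the cut by one patient and leaves the pattern unchanged.

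**The case against.** The strongest reply is that nothing disappears from the report. The example term (11/56 and 2/48) is in the all-TEAE table, which has no cut-off. It also passes both 10% cuts, at 19.6% in one cohort and 12.5% overall. Serious occurrences have their own table. All of this stands. A reader might infer that the rule hides toxicity or undermines the safety and tolerability objective. The documents do not support that: the full tabulations serve the objective, no endpoint rests on this table, and the protocol does not ask for it. What remains is narrower. The other tables either mix serious and non-serious events or show serious ones only. Subtracting the serious count from the total does not give the non-serious count, because one patient can have both kinds of occurrence of the same term.

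The second reply is that genuinely common events are rarely lost by chance. That stands too: at equal true rates the both-cohorts rule lists 97.5% of terms at 15%. It would be wrong to say that frequent events in general drop out by chance. Chance loss is concentrated near the 5% line.

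The third reply is that 'both cohorts' may mean the two combined, since the phase 2 safety layout in SAP 7.1.1 has a Total column. This is possible, and the pooled reading removes most of the loss. But the SAP does not say it, and the neighbouring overall cut is worded without any mention of cohorts. If pooling was meant, the sentence still needs to say so, because two programmers could build different tables from it.

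**Conclusion.** The point holds as a minor defect in a reporting rule. As written, the table omits any non-serious term with 2 or fewer patients in one cohort, however frequent it is in the other. At equal true rates, the chance that a term is listed falls from 96% to 63% at 8%, from 99% to 81% at 10%, and from about 100% to 97.5% at 15%. The loss is larger when the cohorts truly differ. What is lost is the separate non-serious count for those terms; their overall incidence is still reported. No efficacy result, interim rule or data collection is touched.

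This rests on three assumptions: the literal reading of 'both cohorts', safety-population sizes near the 56 and 48 response-evaluable targets, and independent binomial counts. Under a pooled reading the loss is smaller but not zero: 5/56 with 0/48 would still be left out.

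**What to change.** In SAP 7.11.1, change the threshold for this table to: >5% of patients in either cohort, sorted by preferred term. This matches the any-arm rule in the same list and removes the ambiguity. If a pooled cut was intended, the text should say that the 5% applies to all phase 2 patients combined, accepting that terms confined to one cohort can still fall below it. The cost is a word or two in the SAP and a slightly longer table. No new data, derivations or other outputs are needed.

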7.11.2 Clinical Laboratory Evaluations

Whenever available, laboratory values will be assigned toxicity grades using the NCI CTCAE version 4.03. The number and proportion of patients with shifts in NCI CTCAE toxicity grades from baseline to the worst post baseline toxicity grade will be summarized for the following laboratory tests:

- Hematology: Hemoglobin increased, Activated partial thromboplastin time (aPTT) prolonged, INR increased, Lymphocyte count decreased, Lymphocyte count increased, Neutrophil count decreased, Platelet count decreased, White blood cell count decreased.
- Chemistry: Alanine aminotransferase (ALT) increased, Alkaline phosphatase increased, Aspartate aminotransferase (AST) increased, Bilirubin (total) increased, Cholesterol high, Creatinine increased, Gamma glutamyl transferase (GGT) increased, Calcium - decreased, Calcium – increased, Glucose – decreased, Glucose – increased, Potassium – decreased, potassium – increased, magnesium – decreased, magnesium – increased, sodium – decreased, sodium – increased, triglycerides – increased, albumin –decreased, phosphaste – decreased, amylase – increased.

For phase 2 the actual values and change from baseline in clinical laboratory parameters (in SI units) will be summarized for Neutrophils (ANC), Aspartate aminotransferase (AST), Alanine aminotransferase (ALT), Glucose, Hemoglobin A1c, Cholesterol (total), Triglycerides, High-density lipoprotein cholesterol (HDL-C) and Low-density lipoprotein cholesterol (LDL-C) at each scheduled visit up to 6 cycles. Figures of mean actual values at each scheduled visit up to 6 cycles will also be generated for these clinical laboratory parameters (in SI units).

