**MLN0128****Clinical Study Protocol C31001 Amendment 6, EudraCT: 2014-001921-34**

- No evidence of disease progression for  $\geq 3$  months or hemorrhage after treatment.
  - Off-treatment with dexamethasone for 4 weeks before administration of the first dose of MLN0128.
  - No ongoing requirement for dexamethasone or antiepileptic drugs.
5. Eastern Cooperative Oncology Group (ECOG) performance status 0 to 2 (refer to Section 14.1).
  6. Clinical laboratory values as specified below within 4 weeks before the first dose of MLN0128:
    - Bone marrow reserve consistent with absolute neutrophil count (ANC)  $\geq 1.5 \times 10^9/L$ ; platelet count  $\geq 100 \times 10^9/L$ ; hemoglobin  $\geq 9$  g/dL.
    - Total bilirubin  $\leq 1.5$  times the upper limit of the normal range (ULN), aspartate aminotransferase (AST) and alanine aminotransferase (ALT)  $\leq 2.5 \times \text{ULN}$  ( $\leq 5 \times \text{ULN}$  if liver metastases are present).
    - Creatinine clearance  $\geq 50$  mL/min based either on Cockcroft-Gault estimate (refer to Section 14.3) or based on a 12- or 24-hour urine collection.
    - Fasting serum glucose  $\leq 130$  mg/dL and fasting triglycerides  $\leq 300$  mg/dL.
  7. Left ventricular ejection fraction (LVEF) within 5 absolute percentage points of institutional standard of normal as measured by echocardiogram (ECHO) or multiple gated acquisition (MUGA) scan within 4 weeks before the first dose of MLN0128 (ie, if the institutional standard of normal is 50%, LVEF may be as low as 45% to be eligible for the study).
  8. Able to provide paraffin blocks or a minimum of 10 unstained slides of available archival tumor tissues (paraffin blocks are preferred). If archival tumor tissue is not available, a tumor biopsy may be performed before the patient begins treatment with MLN0128. If fewer than 10 slides are available or the tumor content/area requirements are not met, study eligibility will be determined upon discussion with the sponsor.

9. Ability to swallow oral medications, willingness to perform mucositis prophylaxis, and suitable venous access for the study-required blood sampling.
10. Voluntary written consent must be given before the performance of any study-related procedure not part of standard medical care, with the understanding that consent may be withdrawn by the patient at any time without prejudice to future medical care.

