**MLN0128****Clinical Study Protocol C31001 Amendment 6, EudraCT: 2014-001921-34**

- If  $\geq 2$  DLTs occur in the treatment group receiving 2 mg of MLN0128 in combination with either exemestane and/or fulvestrant, the study will be stopped.

Toxicity will be evaluated according to the NCI CTCAE, version 4.03, effective 14 June 2010. These criteria are provided in the Study Manual. A DLT will be defined as any of the following events that are considered by the investigator to be at least possibly related to treatment with MLN0128 in combination with either exemestane or fulvestrant:

- Grade 3 or higher nonhematologic toxicity, despite adequate treatment, except for the following:
  - Grade 3 hyperglycemia lasting  $\leq 14$  days (all patients should receive optimal antihyperglycemic treatment, including insulin).
  - Grade 3 rash lasting  $\leq 3$  days (all patients should receive topical steroid treatment, oral antihistamines, and oral steroids, if necessary).
- Grade 4 neutropenia lasting  $>7$  days in the absence of growth factor support.
- Grade 4 neutropenia of any duration accompanied by fever  $\geq 38.5^{\circ}\text{C}$  and/or systemic infection.
- Any other  $\geq$ Grade 4 hematologic toxicity.
- Inability to administer at least 75% of planned doses of MLN0128 within Cycle 1 due to study drug-related toxicity.
- Any clinically significant occurrence that the investigator and sponsor agree would place patients at an undue safety risk.

Patients who experience an AE that meets the definition of a DLT during or after completing Cycle 1 should have their study drug treatment interrupted. If the event resolves to Grade 1 or baseline values within 2 weeks of interrupting planned therapy, and in the opinion of the investigator and the sponsor's project clinician the benefits of continuing treatment outweigh the risks posed by the toxicity, patients may continue study treatment with MLN0128 at a 25% to 50% dose reduction (ie, dose reduced from 4 mg to 3 mg [25%]; from 3 mg to 2 mg [33%]; or from 2 mg to 1 mg [50%] QD) with approval of the sponsor's project clinician. Alternatively, if dose modification is required for patients receiving 2 mg QD, then the dosing frequency may also be decreased to 5 days per week (28% reduction) instead of

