##### **Hematology/Coagulation**

A blood sample for complete blood count with platelet count and white blood cell (WBC) count with differential will be obtained at the times specified in the [Schedule of Events](#).

The hematology and coagulation panels include the following:

- Hemoglobin
- Hematocrit
- Platelet (count)
- Leukocytes with differential
- Neutrophils (ANC)
- Activated partial thromboplastin time (aPTT)
- Prothrombin time/international normalized ratio (PT/INR)

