#### **8.1.4 Procedures for Handling Missing, Unused, and Spurious Data**

All available efficacy and safety data will be included in data listings and tabulations. No imputation of values for missing data will be performed.

Data that are potentially spurious or erroneous will be examined according to standard data management operating procedures.

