### 8.1.8 Safety Analyses

Safety will be evaluated by the incidence of AEs, severity and type of AEs, and by changes from Baseline in the patient's vital signs, weight, and clinical laboratory results using the safety population. Exposure to MLN0128 and reasons for discontinuation will be tabulated.

TEAEs that occur after administration of the first dose of MLN0128 and through 30 days after the last dose of MLN0128 will be tabulated.

AEs will be tabulated according to the Medical Dictionary for Regulatory Activities and will include the following categories:

- TEAEs.
- Drug-related TEAEs.
- Grade 3 or higher TEAEs.
- Grade 3 or higher drug-related TEAEs.
- The most commonly reported TEAEs.
- SAEs.

A listing of TEAEs resulting in MLN0128 discontinuation will be provided.

Descriptive statistics for the actual values of clinical laboratory parameters (and/or change from Baseline in clinical laboratory parameters) will be presented for all scheduled measurements over time.

Shift tables for laboratory parameters will be generated based on changes in NCI CTCAE grade from Baseline to the worst postbaseline value.

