**MLN0128****Clinical Study Protocol C31001 Amendment 6, EudraCT: 2014-001921-34**

Concomitant medications will be coded using the World Health Organization (WHO) Drug Dictionary. The number and percentage of patients taking concomitant medications will be tabulated by WHO drug generic term by cohort in the safety population.

Additional safety analyses may be performed to more clearly enumerate rates of toxicities and to further define the safety profile.

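### The CTCAE shift list in SAP 7.11.2 carries hemoglobin only as an increase, so the SAP specifies no summary table of graded hemoglobin falls

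*SAP*

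**What the plan says.** Protocol 8.1.8 sets out the purpose of the shift tables: "Shift tables for laboratory parameters will be generated based on changes in NCI CTCAE grade from Baseline to the worst postbaseline value". Hemoglobin is the first item under "The hematology and coagulation panels include the following" in Protocol 7.4.14, so the data are collected.

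SAP 7.11.2 first assigns CTCAE version 4.03 grades to laboratory values wherever a grade is available. It then limits the summary of shifts, from baseline to worst postbaseline grade, to a list of tests. The hematology list starts "Hematology: Hemoglobin increased, Activated partial thromboplastin time (aPTT) prolonged, INR increased", gives lymphocytes in both directions, and ends "Neutrophil count decreased, Platelet count decreased, White blood cell count decreased". There is no entry for low hemoglobin or anemia under hematology or chemistry. The paragraph is not limited to one phase.

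The only other outputs in the section are phase 2 summaries of actual values and change from baseline, with mean plots, for nine selected parameters. Hemoglobin A1c is one of them; hemoglobin is not.

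**The concern.** For a marrow count, the direction of safety interest is normally downward. The protocol's own eligibility rule points the same way: inclusion criterion 6 sets minimum values for neutrophils, platelets and hemoglobin together, as bone marrow reserve. In the shift list, neutrophils and platelets have a row for decreases and hemoglobin does not.

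A table programmed exactly to the SAP would show patients moving to higher grades for high hemoglobin and would have no row for patients moving to higher grades for low hemoglobin. Laboratory values are named separately from adverse events in the phase 1b primary endpoint and in the secondary endpoints (SAP 5.0 and 5.1), so adverse event tables are not meant to be the only view of them. At stake is the completeness of the safety tables. No efficacy result or decision rule depends on it.

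**Working it through.** The plan states no figure to reproduce. The check is a count of the list in SAP 7.11.2 and a comparison with the other places that could show the same information.

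**1. Count the rows.**
- Hematology: hemoglobin up; aPTT; INR; lymphocytes down; lymphocytes up; neutrophils down; platelets down; white cells down = 8.
- Chemistry: ALT, alkaline phosphatase, AST, bilirubin, cholesterol, creatinine, GGT, triglycerides and amylase, each up = 9; calcium, glucose, potassium, magnesium and sodium, each down and up = 10; albumin and phosphate, each down = 2. Total 9 + 10 + 2 = 21.
- All rows: 8 + 21 = 29.

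**2. Count the rows for decreases.** Hematology 4 (lymphocytes, neutrophils, platelets, white cells) plus chemistry 7 (calcium, glucose, potassium, magnesium, sodium, albumin, phosphate) = 11. Hemoglobin contributes 0.

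**3. Ask whether the hemoglobin entry could cover both directions.** Six tests are named once for each direction: lymphocytes, calcium, glucose, potassium, magnesium and sodium. The list's own convention is therefore to write a second entry when the second direction is wanted. Hemoglobin has one entry, upward.

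**4. Compare the blood counts in the list.**

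| Count | Decrease row | Increase row |
|---|---|---|
| Lymphocytes | yes | yes |
| Neutrophils | yes | no |
| Platelets | yes | no |
| White cells | yes | no |
| Hemoglobin | no | yes |

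Four of five have a decrease row. Hemoglobin is the only one listed solely as an increase, which is the pattern expected from a slip in one word.

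**5. Look for another summary of graded falls.**
- The phase 2 value and change summaries (SAP 7.11.2) leave out hemoglobin and are ungraded. They also leave out platelets and white cells, so that list is a deliberate selection and is not criticized here.
- Adverse event tables (SAP 7.11.1) show a laboratory fall only if it became an adverse event. Protocol 9.1.2 requires that it led to discontinuation, delay, dose modification or intervention, or was judged a clinically significant change. Protocol 9.2 adds any clinically relevant deterioration.
- DLTs (Protocol 6.2) include other related hematologic events at or above "Grade 4 hematologic toxicity". This applies to phase 1b only, and the SAP listing covers Cycle 1.
- SAP 7.13 declares one change, on exemestane pharmacokinetics, and nothing on hemoglobin.

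None of these is a specified summary of graded hemoglobin falls drawn from the laboratory data.

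**The case against.** The strongest reply is that little is lost. SAP 7.11.2 grades laboratory values without restriction by test, so graded hemoglobin should exist in the data and only a summary row is absent. Falls that mattered clinically should reach the adverse event tables, including the table of Grade 3 or higher events. The protocol also says "All available efficacy and safety data will be included in data listings and tabulations" and "Additional safety analyses may be performed to more clearly enumerate rates of toxicities". A programmer might notice the slip.

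Most of this stands, and it limits the point. It does not remove it. The two general sentences name no hemoglobin row, and relying on someone to notice is weaker than correcting the text.

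A reader might go further than the documents allow in three ways.

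- *That the SAP breaches Protocol 8.1.8.* That section promises shift tables for laboratory parameters; it does not promise every parameter in both directions. The SAP list is a selection: hematocrit, urea nitrogen, urate and lactate dehydrogenase are collected and have no row either. The fair statement is that a test which was selected is shown in a direction that does not serve the purpose of the table. Nor does the general sentence in Protocol 8.1.4 create a specific breach.
- *That hemoglobin falls would be visible only as adverse events or DLTs.* This cannot be established. Two listing entries in SAP 9.0 are redacted, and Protocol 8.1.8 also provides for descriptive statistics of laboratory parameters over time, although these are ungraded and the SAP narrows them.
- *That the eligibility floor proves which tables were intended.* It shows an interest in low values at entry, no more.

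**Conclusion.** The SAP is wrong as written on this entry. Followed literally, neither phase has a shift row for falls in hemoglobin, and no summary table of graded falls from laboratory data is specified in the visible text. The gap is 1 missing row beside 29 existing ones. It applies to the shift tables for all planned patients, 24 + 56 + 48 = 128, but that is the denominator of the tables and not a count of patients harmed or missed. The number with graded falls that did not become adverse events cannot be derived from the documents.

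The practical loss is mainly a summary of falls that led to no action and were not judged clinically relevant, together with a view of hemoglobin that does not depend on investigator reporting. The conclusion should not be read as anemia going unreported.

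It rests on two assumptions: that the list is closed, as its wording indicates, and that the redacted text holds no such table. That the cause is a wrong word is an inference from the pattern of the other blood counts; the omission needs correcting whatever the cause.

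**What to change.** In SAP 7.11.2, add *Hemoglobin decreased (anemia)* to the hematology shift list for phase 1b and phase 2. Keep the increase entry only if it was also intended; otherwise replace it. No change to the protocol or to the phase 2 value and change list is needed for this point.

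The cost is one SAP line and one row in each shift table. Hemoglobin is already collected under Protocol 7.4.14, so there are no new data, and efficacy analyses, alpha and power are unaffected.
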